1.0 Background & Rationale

Antibody-mediated rejection (ABMR) is a unique, significant and often severe form of allograft rejection. ABMR is characterized by several pathologic variants that are often resistant to treatment with standard immunosuppressive medications. Significant advances have occurred in our ability to predict patients at risk for and to diagnose ABMR ^{1,2}. The pathophysiology of ABMR suggests a prime role for antibodies, B-cells and plasma cells. As a result, IVIG, rituximab, and/or plasmapheresis (PLEX) have been leveraged for the treatment of acute ABMR³⁻⁷. Despite the success of these therapies, post-transplant ABMR, chronic active ABMR (cABMR), and transplant glomerulopathy (TG) remain significant problems that are often unresponsive to current therapies⁴. Data from the Deterioration in Kidney Allograft Function (DeKAF) study show that most graft losses in the current era of immunosuppression have evidence of cABMR with positive C4d staining^{2,8}. It is estimated that 5,000 renal allografts are lost each year in the US, primarily from cABMR and TG⁹. The current treatment paradigms rely on reduction of antibody levels to prevent ABMR. This raises the importance of maintaining immunosuppression and investigating novel methods to prevent and treat ABMR/cABMR that directly address the reduction of donor specific antibodies (DSAs) and antibody producing cells.

ABMR is frequently seen in patients receiving inadequate immunosuppression or who are noncompliant with anti-rejection medications and those who receive human leukocyte antigen (HLA)-incompatible transplants. In addition, TG is a known consequence of persistent DSA positivity which rapidly dissipates allograft function, resulting in graft failure and return to dialysis with attendant emotional consequences for the patients and financial consequences for the health care system ¹⁰⁻¹⁴. No current therapy is FDA approved and patients are often treated with combination therapies that make analysis of efficacy difficult. Thus, there is a large unmet clinical need. To this end, it is imperative that novel therapies to prevent immunologic injury to the microcirculation be developed and studied in patients with cABMR and TG.

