3.0 Primary Objectives

This study will be an open label design to assess the safety and efficacy of clazakizumab 25 mg SC given every 4 weeks (30 days) for a total of 6 doses in eliminating DSAs and stabilizing clinical features of cABMR in patients who have biopsy proven severe cABMR +TG. If improvements are seen in pathologic features of antibody mediated rejection from this biopsy compared to index biopsy, we will offer patients the opportunity to continue clazakizumab administrations monthly for an additional 6 months. A one year biopsy will then be performed at the end of the study. Safety determinations will be aimed at assessments of any side effects associated with clazakizumab administration and risk for infectious complications associated with clazakizumab therapy. Limited efficacy determinations will include assessment

of composite surrogate end points including patient and graft survival, stabilization of the clinical features of cABMR (eGFR, SCr) after clazakizumab treatment, and safety throughout study duration.

Long term primary objectives include:

- 1. assess the safety and efficacy of clazakizumab 12.5 mg or 25 mg SC given every 4-8 weeks in eliminating DSAs and stabilizing clinical features of cABMR in patients who have biopsy proven severe cABMR +TG
- 2. assess composite surrogate end points including patient and graft survival, stabilization of the clinical features of cABMR (eGFR, SCr) after clazakizumab treatment, and safety throughout study duration

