3.2 Inclusion Criteria

- ✓ Age 15-75 years at the time of screening.
- ✓ Biopsy proven cABMR with TG on biopsy as defined by Banff 2015 and DSA + at time of biopsy
- ✓ Subject/Parent/Guardian must be able to understand and provide informed consent.
- ✓ Pneumococcal vaccinated
- ✓ Negative tuberculin ppd result or negative Quantiferon TB gold

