3.3 Exclusion Criteria

- ✓ Multi-organ transplant (e.g. kidney and pancreas)
- √ eGFR < 30 mL/min/1.73m²
- ✓ Advanced Transplant Glomerulopathy (CG3) or advanced IFTA (ct or ci scores ≥3)
- ✓ Previous allergic reactions to monoclonal antibodies.
- ✓ Lactating or pregnant females.

- ✓ Women of child-bearing age and male partners of women of child-bearing age who are not willing or able to practice FDA-approved forms of contraception during study and for 5 months after last dose.
- ✓ HIV-positive subjects.
- ✓ Subjects who test positive for HBV by HBVeAg/DNA or HCV infection [positive Anti-HCV (EIA) and confirmatory HCV RIBA].
- ✓ Subjects with latent or active TB. Subjects must have negative Quantiferon TB gold test result.
- ✓ Recent recipients of any licensed or investigational live attenuated vaccine(s) within two months of the screening visit (including but not limited to any of the following:
 - o Adenovirus [Adenovirus vaccine live oral type 7]
 - Varicella [Varivax]
 - Hepatitis A [VAQTA]
 - Rotavirus [Rotashield]
 - Yellow fever [Y-F-Vax]
 - Measles and mumps [Measles and mumps virus vaccine live]
 - Measles, mumps, and rubella vaccine [M-M-R-II]
 - Sabin oral polio vaccine
 - Rabies vaccines [IMOVAX Rabies I.D., RabAvert])
- ✓ A significantly abnormal general serum screening lab result defined as a WBC < 3.0 X 10³/ml, a Hgb < 8.0 g/dL, a platelet count < 100 X 10³/ml, an SGOT or SGPT > 3X upper limit normal
- ✓ Individuals deemed unable to comply with the protocol.
- ✓ Subjects with active CMV or EBV infection as defined by CMV-specific serology (IgG or IgM) and confirmed by quantitative PCR with or without a compatible illness (Quantitative PCR cut off defined as having > 50 copies of CMV or EBV DNA/PCR)
- ✓ Use of investigational agents within 4 weeks of participation.
- √ History or active Inflammatory Bowel Disease or Diverticular Disease or gastrointestinal perforation
- ✓ Recent infection (within past 6 weeks of screening) requiring any antibiotic use (oral, parenteral or topical).
- ✓ Present or previous (within 5 years) malignancy except for basal cell carcinoma, fully excised squamous cell carcinoma of the skin or non-recurrent (within 5 years) cervical carcinoma-in-situ.

4. Study Design & Methods

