Background: This is a single center, Phase I/II, open label single-arm exploratory study. The trial will primarily examine the safety and tolerability of clazakizumab given after the diagnosis of cABMR in 10 subjects (15-75yrs) who exhibit DSAs to their donor. Patients entered will also have been diagnosed with cABMR + TG post-transplant based on Banff 2015 criteria. Patients are required to have a eGFR \geq 30 mL/min/1.73m² as calculated by the MDRD equation (Schwartz equation will be used to estimate CrCl for patients under 18 years of age) at entry. All patients will be recruited from the renal transplant program at Cedars-Sinai Medical Center. Once cABMR is diagnosed, donor-specific anti-HLA antibodies will be assessed (DSA) which are associated with cABMR and/or graft loss. DSA will be detected using solid phase assay systems currently utilized at the Cedars-Sinai Medical Center HLA Laboratory ([name] Director, [contact]. These anti-HLA antibodies may result naturally or from previous pregnancy, transfusions, or prior transplants. Patients treated with clazakizumab for cABMR will have labs for DSAs, and other monitoring labs as well as immunologic studies as outlined (See Study Protocol in Appendix A). In addition to the standard post-transplant immunosuppressive protocol, patients with cABMR will receive clazakizumab 25mg SC given every 4 weeks (30 days) for a total of 6 doses. If no safety/tolerability/efficacy issues are observed after the initial dose, patients will continue the protocol as outlined (see Appendix A). A protocol biopsy will be performed after the 6th and after the 12th doses of clazakizumab (as mentioned before) to assess the allograft for evidence of cABMR/ABMR, including C4d staining and TG using Banff 2015 criteria¹⁴. Banff scoring will be compared between the index and protocol biopsy after cessation of therapy. Patients who have evidence of persistent allograft dysfunction may have non-protocol biopsies for cause. After completion of the clazakizumab therapy, patients will be followed up to assess allograft function and ABMR episodes as well as DSAs. The protocol is summarized in figure 14 below. Monitoring of Treg, Thir, Tfh and plasmablast as well as IL-6

and CRP level will be performed in the Transplant Immunology Lab at Cedars-Sinai Medical Center at select time points ([name] Director, [contact]).

[figure not shown]

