As indicated previously, the study will be halted and re-evaluated by the Data and Safety Monitoring Board (DSMB) if any patient in the study group develops SAEs or evidence of severe infusion related or infectious complications. In addition the study will be reevaluated if a patient develops worsening ABMR while in treatment, possibly indicating lack of efficacy of clazakizumab (see appendix C).

7 Statistical Analysis

Due to the exploratory nature of this study that involves safety endpoints only and the small sample size that is not powered for efficacy end points, our primary objective will be to assess safety end points and limited efficacy. Most important will be tolerability in the ESRD population and determination of the effects of clazakizumab treatment on circulating DSAs as well as the ability to improve outcomes of patients with cABMR and TG. We will however plan to assess biopsies 6M post-transplantation in patients desensitized with clazakizumab treatment to determine if there are durable effects in prevention of ABMR both acute and chronic.

8 References

- 1. Colvin RB. Antibody-mediated renal allograft rejection: diagnosis and pathogenesis. J Am Soc Nephrol 2007;18:1046-56.
- 8. Sellarés J, de Freitas DG, Mengel M, et al. Understanding the causes of kidney transplant failure: the dominant role of antibody-mediated rejection and nonadherence. Am J Transplant 2012;12:388-99.

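### The qualifying biopsy is also the Banff baseline, with no masked reading provided for: selection biases required activity scores towards improvement and ci/ct towards worsening

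*Protocol*

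**What the plan says.** Section 3.2 admits patients on the index biopsy: "Biopsy proven cABMR with TG on biopsy as defined by Banff 2015 and DSA + at time of biopsy". Section 3.3 also sets a ceiling by excluding "Advanced Transplant Glomerulopathy (CG3) or advanced IFTA (ct or ci scores ≥3". Section 4 then makes the same biopsy the comparator: "Banff scoring will be compared between the index and protocol biopsy after cessation of therapy".

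Section 4 states that "This is a single center, Phase I/II, open label single-arm exploratory study", with "10 subjects (15-75yrs) who exhibit DSAs to their donor". No control group is available to show how scores move without the drug. The visible text mentions no masked, shuffled, duplicate or central slide reading.

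The comparison has two uses. Change in Banff 2015 features at six months is among the major secondary objectives (Section 3.1) and is named again in the text after Figure 14. It also contributes to the offer of six further months, which Section 3.0 introduces with "If improvements are seen in pathologic features of antibody mediated rejection from this biopsy compared to index biopsy". The Figure 14 legend and the Appendix A footnote list eGFR, DSA and the investigator's confirmation beside the biopsy.

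**The concern.** A score that had to reach a threshold for entry carries, on average, some error in the direction of that threshold. A later independent reading does not share the error, so the score moves back even if the graft is unchanged. In addition, a reader who knows that a slide comes from a month-6, on-drug biopsy may score it differently. Without a control arm, neither effect can be told apart from a drug effect.

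The within-patient histology result is at stake. Section 1.4.2 cites a comparison of the same kind, falls in C4d and g + ptc in 9 tocilizumab patients biopsied again at one year. The new result is therefore likely to be reported and relied on.

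**Working it through.** The protocol states no power, alpha or effect size for histology, so there is no figure of its own to reproduce. The check asks how far a score would move with no drug effect and no natural change.

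**Inputs from the protocol.** Lower bound: the diagnosis must be present (3.2). Upper bound: cg3, or ct or ci of 3 or more, is excluded (3.3). n = 10 and no control arm (4).

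**Assumed inputs, not in the documents.** Correlation ρ between the index and follow-up readings: 0.4 to 0.8. Reader share f of the variance that the two readings do not share: 0.25 to 0.75. Entry cut-offs: between -1 and +1.5 SD of the source population.

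**Formulas**, in SD of one reading, for a standard normal score Z:

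- Expected change = -(1 - ρ) × E[Z | selected].
- After a masked re-read of the index slide, with nobody reselected: -(1 - ρ)(1 - f) × E[Z | selected].
- Lower bound c only: E = φ(c) / (1 - Φ(c)).
- Upper bound u only: E = -φ(u) / Φ(u).
- Both bounds: E = (φ(c) - φ(u)) / (Φ(u) - Φ(c)).

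**Worked example, ρ = 0.6**

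- Required activity feature, c = 0: E = 0.3989 / 0.5 = 0.798. Change = -0.4 × 0.798 = -0.32. After the re-read with f = 0.5: -0.16.
- ci or ct, u = 1: E = -0.2420 / 0.8413 = -0.288. Change = +0.12.
- cg, c = 0 and u = 1: E = 0.460, change -0.18. With c = -1 and u = 0.5: E = -0.207, change +0.08.

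**Full range**

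| Score | Selection | Cut-offs (SD) | Expected change (SD) |
|---|---|---|---|
| Activity feature required for entry | lower bound | -0.5 to +1 | -0.10 to -0.92 |
| ci, ct | upper bound | +0.5 to +1.5 | +0.03 to +0.31 |
| cg | both bounds | -1 to +1.5 | -0.37 to +0.12 |

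After the masked re-read, the first row becomes -0.03 to -0.69 SD.

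**Check on a 0-3 ordinal score**, by simulation with 400,000 draws per scenario, selecting at 1 or more, over the same range of ρ:

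| Reading | Mean change (points) | Reads improved | Reads worse |
|---|---|---|---|
| Index reading as baseline | -0.08 to -0.45 | 25% to 51% | 13% to 25% |
| Masked re-read, f = 0.5 | -0.03 to -0.17 | 23% to 38% | 20% to 29% |

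With the index reading as baseline, about 3 to 5 of 10 unchanged patients would read as improved and about 1 to 3 as worse. For scale, the standard error of a mean change in 10 patients is about 0.2 to 0.3 points, so the artefact ranges from well below one standard error to somewhat above it.

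**The case against.** - **Selection is not one-sided.** A reader might infer that Banff scores in general are expected to improve, and so that the bias favours the drug. The documents do not support this. The Section 3.3 ceiling pushes ci and ct the other way, and cg, the transplant glomerulopathy score, is bounded on both sides. This stands and limits the point to activity features required for entry.
- **Progression opposes improvement.** Section 1.0 says that "TG is a known consequence of persistent DSA positivity which rapidly dissipates allograft function", and the Figure 1 legend puts graft loss at about half by 1.9 years after diagnosis. The net untreated change therefore cannot be signed. This also stands, though an offsetting trend of unknown size does not make the comparison easier to interpret.
- **Masking may be arranged elsewhere.** A SAP or pathology manual may cover it, and the copy at hand does not show the footnote attached to the screening biopsy in Appendix A. Section 4 compares the two biopsies without saying which reading of the index slide is used. The point therefore rests on absence from the visible text.
- **Histology is not the main measure.** Section 3.1 places it among the secondary objectives, and Section 7 stresses tolerability, DSAs and patient outcomes. A reader might also infer that the biopsy alone decides who continues, but it is one of several inputs and the Section 4 text also accepts stabilization.
- **No test is planned.** Assuming repeat-score reliability of 0.5 to 0.8 and a selected mean 0.5 to 1 SD high, a two-sided 5% paired t-test in 10 patients would be significant with no drug effect in 7% to 29% of trials. The protocol proposes no such test and describes a "small sample size that is not powered for efficacy end points". The calculation also treats ordinal scores as normal and ignores the narrowing of variance by selection, so it is not a property of this trial.

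Being exploratory excuses low precision. It does not excuse a systematic error that is cheap to reduce.

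**Conclusion.** The point holds in a limited form. The biopsy that qualifies the patient is also the Banff baseline, nothing absorbs regression to the mean, and no masked reading is visible. With no drug effect and no progression, required activity features drift towards improvement and ci/ct towards worsening; cg may move either way. Expectation bias can be added to any of them.

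The sizes rest wholly on assumed agreement and cut-offs and serve as illustration. They do not show that the trial's result will be wrong. Masked re-reading is a modest, cheap improvement to a named secondary measure in a 10-patient exploratory study.

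**What to change.** Keep the live readings for decisions about patients. For the analysis of change in Banff scores:

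- Have the center's existing pathologist re-read all index, month-6 and month-12 slides in random order, with patient and time point masked.
- Use these readings for both baseline and follow-up, without reselecting patients on the new index reading.
- Report activity and chronicity scores separately, since selection pulls them in different directions.
- State that biopsy-sampling regression to the mean, natural progression and the co-treatment in Section 5 (pulse methylprednisolone, plasmapheresis and high-dose IVIG) remain inseparable from a drug effect.

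The cost is one reading session of at most about 30 existing biopsies (10 patients × 3 time points), with no new biopsy and no extra reader. The apparent improvement in activity scores may turn out smaller. The re-read does not alter the live month-6 continuation reading.

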Figure 14: This figure shows the protocol designed to investigate the safety and efficacy of clazakizumab in treating cABMR + TG. The study is open label, single center one-arm study that will enter patients diagnosed with cABMR + TG by renal biopsy and who have eGFR of > 30cc/min at time of diagnosis. Entered patients will receive clazakizumab 25mg every 4 weeks (30 days) for a total of 6 doses. If patients show improvement (ie: eGFR/DSA/biopsy/PI confirmation) they will continue monthly clazakizumab for an additional 6 months and will have a second biopsy at 12 month protocol. Immunologic and viral monitoring labs will be performed as indicated. For those continuing in the long term extension, the day 365 visit will be followed by visits every 4-8 weeks.

The subjects will be followed to determine if the use of clazakizumab for treatment of cABMR in this high-risk transplant population is safe and without infectious risks. In addition, we will determine the effects of clazakizumab treatment on renal biopsy assessments performed at 6 months. Assessments of renal function, donor specific antibody, and Banff 2015 biopsy scores will be evaluated at that time. If improvement or stabilization observed, clazakizumab will be resumed monthly x 6 doses (starting day 180 to day 330) and last study visit will be day 365 with biopsy for those who are not continuing to the long term extension. For those continuing in the long term extension, the day 365 visit will be followed by visits every 4- 8 weeks, per the schedule in Appendix E. We will assess the transplanted patients to determine the number who sustain a viable and functioning kidney allograft as well. In the event a patient does not show improvement after receiving 6 doses of clazakizumab, no further treatment will be given and the patient will return at Day 365 for a final study visit. All subjects will be evaluated on an intent-to-treat basis. The subject accrual rate will be limited to 2 patients for the initial dosing appointment. Once the first 2 patients have received their first injection, 2-4 patients may be screened per month until all 10 patients are enrolled. Repeat laboratories will be performed at the completion of clazakizumab therapy to determine effect on levels and correlation with any potential events. A detailed analysis of the study is discussed below.

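### After six doses, Section 4 tells a stable but non-improved patient both to continue and to stop clazakizumab, and the same conflict decides who has the 12-month biopsy

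*Protocol*

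**What the plan says.** The continuation decision after the first six doses is described in four places.

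- **Section 4, main text after Figure 14.** Continue: "If improvement or stabilization observed, clazakizumab will be resumed monthly x 6 doses". Stop, later in the same paragraph: "In the event a patient does not show improvement after receiving 6 doses of clazakizumab, no further treatment will be given". The stopped patient returns at Day 365 for a final visit.
- **Section 4, Figure 14 text.** "If patients show improvement (ie: eGFR/DSA/biopsy/PI confirmation) they will continue monthly clazakizumab for an additional 6 months", with a second biopsy at 12 months.
- **Section 3.0.** A further six months is offered under this condition: "If improvements are seen in pathologic features of antibody mediated rejection from this biopsy compared to index biopsy". The same section lists among its efficacy determinations "stabilization of the clinical features of cABMR (eGFR, SCr) after clazakizumab treatment".
- **Appendix A, footnote marked with two asterisks.** Continuation rests on the protocol biopsy results, better GFR, better DSA, and/or PI confirmation. The footnote then sends a patient without improvement straight to the Day 365 visit.

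On the 12-month biopsy, Section 3.1 restricts it to patients who receive 12 doses, and the Appendix A schedule gives the Day 365 biopsy the same double asterisk as the continuation visits.

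**The concern.** The Section 4 continue sentence treats improvement and stabilization as two separate states, either of which leads to six more doses. The stop sentence names improvement only and does not exempt a stable patient. Someone whose disease has neither improved nor worsened at six months therefore meets the condition of both sentences, and whichever is followed, the other is breached.

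This is not a remote case. Stabilization of renal function is one of the trial's own stated aims, so a stable patient is an outcome the treatment is meant to produce. At stake are six further doses of an investigational antibody, a second protocol biopsy, and the ability to say afterwards whether the patient was treated according to protocol. In a 10-patient study whose main purpose is safety and tolerability, exposure should not depend on which sentence the reader happens to apply.

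**Working it through.** **Step 1. Reproduce the dose counts.** In 30-day steps, the first course falls on days 0, 30, 60, 90, 120 and 150, which is 6 doses. The second falls on days 180, 210, 240, 270, 300 and 330, again 6. The total is 6 + 6 = 12, as the protocol states.

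**Step 2. Apply each rule to a patient who is stable and improved on no marker.**

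| Place | Condition for continuing | Result for this patient |
|---|---|---|
| Section 4, continue sentence | improvement or stabilization | continues: 12 doses, 12-month biopsy |
| Section 4, stop sentence | improvement | stops: 6 doses, no 12-month protocol biopsy |
| Section 4, Figure 14 text | improvement, glossed as eGFR, DSA, biopsy, PI confirmation | not met on the markers; open if PI confirmation alone is enough |
| Section 3.0 | improvement in pathologic features | no offer made |
| Appendix A footnote | biopsy results, GFR, DSA, and/or PI confirmation; ends if no improvement | open through PI confirmation, then closed by the next sentence |

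Only the first row mentions stabilization as a ground for continuing. No place says that one rule overrides another.

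**Step 3. Follow the consequence.** Section 3.1 and the Appendix A schedule tie the 12-month protocol biopsy to the second course. The patient in Step 2 therefore has it or does not have it according to the same unsettled choice.

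**Step 4. Gauge the reach.** The protocol gives N = 10 and 6 doses in the second course. It does not give the share *s* of patients who are stable and improved on no accepted marker, so *s* is assumed.

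- Expected patients: 10 × *s*
- Doses in question: 6 × 10 × *s*
- Chance of at least one case: 1 − (1 − *s*)^10

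| *s* (assumed) | Expected patients | Doses in question | Chance of at least one |
|---|---|---|---|
| 10% | 1 | 6 | 1 − 0.9^10 = 65% |
| 20% | 2 | 12 | 1 − 0.8^10 = 89% |

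**Step 5. Check what is not affected.** In Appendix A the Day 180 biopsy and the Day 365 eGFR, DSA and graft-loss review are marked for every patient, without the double asterisk.

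**Step 6. Compare Section 7 with the rest.** Section 7 speaks of biopsies six months after transplantation in patients desensitized with clazakizumab, to look for prevention of ABMR. Section 3.2 and Section 4 enrol patients who already have biopsy-proven cABMR with TG, and Appendix A times the biopsy at Day 180 from the first dose. Neither the population nor the time point in Section 7 is this trial's. This misstatement is separate from the continuation conflict and lends it no weight.

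**The case against.** The best counter-argument is that the PI can resolve each case. The Figure 14 text places PI confirmation inside its gloss of improvement, and the Appendix A footnote joins it with and/or. At a single centre that offers a textual route by which a stable patient might continue. This stands in part: it is too strong to say that every stable patient receives irreconcilable instructions. But the stop sentence in Section 4 does not mention PI confirmation, the footnote's next sentence also ends treatment without improvement, and nowhere is it said that confirmation alone suffices.

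The stop sentence might also be meant loosely as the complement of the continue sentence, that is, neither improved nor stable. The same paragraph uses the two words as different states, so this is a guess at intent and not what is written.

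Some stronger readings are tempting but are not supported.

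- *A large fraction of the cohort is caught.* The conflict reaches only patients improved on none of the accepted markers. For illustration, if any one of three independent markers sufficed and each improved in half of patients (assumed), 0.5^3 = 12.5% would improve on none, or 1.25 of 10. Under such a gate, stable shares far above this could not occur.
- *12-month histology from continuers breaches the statement "All subjects will be evaluated on an intent-to-treat basis".* Restricting that biopsy to patients with 12 doses is stated design in Section 3.1 and Appendix A, and how such data are labelled is commonly left to an analysis plan. Any figure for the resulting selection would rest wholly on assumptions.
- *Extension patients miss the Day 365 biopsy.* The words "last study visit will be day 365 with biopsy for those who are not continuing to the long term extension" more naturally qualify which visit is the last. Section 3.1, the Figure 14 text and Appendix A give continuers the biopsy with no exception for the extension.
- *The Banff comparison after cessation of therapy has no time point.* Section 4 elsewhere says "we will determine the effects of clazakizumab treatment on renal biopsy assessments performed at 6 months", and the first course ends at Day 150 before dosing is resumed. Insisting on index versus Day 180 as the only comparison would be a preference.

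**Conclusion.** The contradiction in Section 4 is real and should be removed. It applies to a patient who is stable at six months and improved on no accepted marker. PI confirmation narrows it in practice but does not settle it, because no passage gives either sentence precedence.

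The number of patients affected is unknown. At an assumed share of 10% to 20%, it is 1 to 2 of 10 patients and 6 to 12 doses, with a 65% to 89% chance that the case arises at least once. These figures show reach only; the contradiction does not depend on them.

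The consequences are for treatment received, for who has the 12-month biopsy, and for judging protocol compliance. The study is exploratory and not powered for efficacy, so no hypothesis test is affected. The Day 180 histology and the Day 365 assessments scheduled for all patients are not subject to this conflict. The Section 7 wording is a separate, plain misstatement.

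**What to change.** Reconcile Section 3.0, Section 4 (the main text and the Figure 14 text) and the Appendix A footnote into one continuation rule, worded identically wherever it appears. The rule should state explicitly:

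1. what happens after six doses to a patient who is stable but not improved; and
2. whether PI confirmation alone is enough to continue.

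Which way these are decided is a clinical choice for the investigator. Once they are decided, eligibility for the 12-month biopsy follows from Section 3.1 without further change.

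Separately, rewrite the biopsy sentence in Section 7 so that it refers to patients with cABMR and TG and to the Day 180 biopsy.

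The cost is protocol wording only. These edits in themselves ask for no extra visit, biopsy or patient.
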